Generally, criterion validity is based on evaluation of the correlation of the measure, or its constituent constructs, to an external measure. Evaluative criteria are correlation coefficients between individual BHI domains and data external to the BHI, with the specific correlation statistic being determined by the variable types. Method refers to a measurement procedure which includes consideration of both data source as well as data collection method. The referent data source for this validation is the BHI respondent self-report and the referent method is a self-administered survey. Utilization of the Multitrait-Multimethod matrix (MTMM) allows evaluation of correlation within (monomethod) and between (heteromethod) methods and sources that are related to within (convergent) and between (divergent) dimensions or traits.¹⁷

Subjective or “softer” levels of evidence are correlation of the intended measure (the BHI) to other measures derived from the same source and using the same method of data collection, such as the correlation of the symptom specific construct of the BHI with a validated measure of symptom severity measure based on respondent self-report. Higher levels of evidence are

required for higher standards of criterion validity of the BHI i.e., a higher level of evidence requires correlation of the BHI with multiple external and independent sources, as well as objective, independent measures, such as a quantified standing (provocative) paper towel test for stress incontinence, post-void residual and uroflow parameters. The needs for correlation of BHI scores with external and independent measures and methods requires having access to these clinical measures for BHI respondents. Study design, including sampling and recruitment (clinical evaluation sample), is dictated by this need.

The PLUS BHS is intended to measure bladder health in *both* the general population and clinical research. Additionally, the validated BHS is intended to be used in a self-administered via paper and pencil (PAPI) mode and an electronic/computer assisted (CASI) mode. As such, this study aims to validate the BHI using samples from two distinct recruitment populations (general population sample and local clinical research center sample) and assessing the two modes of administration within each.

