sample due to the low benefit to cost ratio of this measure in a general population where an external, independent clinical evaluation to interpret volume measure is not possible.

IV.D.5. Clinical tests

Clinical tests will be carried out by PLUS research site designated staff. Designated staff will be required to complete test administration training designed by PLUS clinical investigators.

- Height and weight measurement
- Quantified standing (provocative) paper towel test (PTT) for stress incontinence²⁵
- Non-instrumented seated uroflowmetry with a comfortably full bladder (min 150 mL) including print out of voided volume, urine flow time, and maximal and average urine flow rates.
- Non-invasive pre and post-void residual bladder scan
- Urine analysis (a.k.a. dipstick): pH, specific gravity, blood, glucose, protein, leukocyte and nitrites

IV.D.5.A Paper Towel Test (PTT)

The PTT will be conducted as part of the clinical tests to assess for stress incontinence. The PTT quantifies the amount of leakage as a continuous level variable. By using an ordinary standardized trifolded brown paper towel, even a small volume of urine loss down to a fraction of a drop spreads into a readily observable and measurable wetted area. All PTT will be conducted with a consistent brand of paper towels provided for this study.

Procedure:

- The clinical evaluator will need to be present to ensure proper completion of the PTT and to collect and measure the area on the towel within 10 seconds of completing the test.
- The test will be performed with a comfortably full bladder confirmed by the participant's sensation of fullness and by a bladder volume of ≥ 150 mls indicated on the BladderScan ultrasound
- Wash/sanitize hands and put on gloves.
- Place a blue pad (chux) on the floor for participant to stand on.
- Ask the participant to stand on the blue pad, with feet shoulder width apart.
- With the folded paper towel flat in your palm, ask the participant to place the paper towel lightly against the perineum (advise that the test is being done to demonstrate leakage and hence don't press on the perineum to hold back leakage).
- Be sure the participant keeps the trifold paper towel flat in their palm, and does not fold it over onto itself to create a thicker towel.

- Instruct the participant to do 3 single hard coughs.
- With gloved hands, take the paper towel from the participant and lay it on the counter for measurement within 10 seconds of the test.

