- Observe and mark the paper towel with a determination of results as follows:
 - Observe the towel carefully! Sometimes vaginal secretions are transferred to the paper towel. These are noticeable as a shiny substance sitting on the surface of the towel and poorly absorbed into the towel. It is readily distinct from the dark wetted area of urine. These towels should be marked with a large **X** on the towel for no urine leakage.
 - If the towel is unmarred with vaginal secretions or with wetted area from urine, these towels should be marked with a large **X** on the towel for no urine leakage.
 - If the towel is wet from urine loss, at 10 SECONDS outline the wetted area using a ball-point pen to trace around it. If there is more than one wetted area (sometimes over the 3 coughs leakage hits a different spot on the towel), outline each of the wetted areas. Ignore that the wetted area will continue to spread beyond the marked area after 10 seconds in cases of higher volume leakage. By protocol, wetted area is determined at 10 seconds or less.
 - Using a clear plastic ruler, measure the longest and widest diameter of the circled wetted area, in millimeters (mms). If there are additional circled wetted areas, only measure and record the circled area longest and widest diameter
 - i. Do not attempt to calculate wetted area by hand. Rather, record separately the length of the wetted area and the width of the wetted area on a data collection form.
 - ii. Note the measurements on the Clinical Test Form under **#2 Paper Towel Test:**
 - Mark Overflow if there is any circled wetted area that ran off the edge of the paper towel
 - Length in mm: _____
 - Width in mm: _____
 - If the Paper Towel Test is not completed, check Not done and write an explanation in the space provided
- 2. After the PTT is completed, the participant should be offered towels for cleaning and/or patting dry, as needed, and a chance to wash her hands.

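### The paper towel test is meant to quantify the amount of leakage, but when coughs wet several spots only one is measured; the loss cannot be recovered later, though its effect on validity is probably small

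*Protocol*

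**What the plan says.** All of the procedure is in Protocol section IV.D.5.A (Paper Towel Test).

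- Purpose: "The PTT quantifies the amount of leakage as a continuous level variable".
- Provocation: "Instruct the participant to do 3 single hard coughs", all onto one towel.
- Several spots are expected, because "sometimes over the 3 coughs leakage hits a different spot on the towel", and staff must outline each of them.
- Recording rule: "If there are additional circled wetted areas, only measure and record the circled area longest and widest diameter".
- Staff are not to work out the area by hand. They are to "record separately the length of the wetted area and the width of the wetted area on a data collection form". The listed form entries are one length in mm, one width in mm, an overflow tick and a not-done tick.
- The overflow tick reads: "Mark Overflow if there is any circled wetted area that ran off the edge of the paper towel".

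The role of the test is set in section IV.A (Validation approaches), which names it among the "objective, independent measures, such as a quantified standing (provocative) paper towel test for stress incontinence, post-void residual and uroflow parameters". Section IV.E.2.c (External Criterion Validity) counts the clinical tests as hard measures supporting the high standard of evidence. It judges convergent validity by correlations of at least 0.20.

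**The concern.** The stated quantity and the recorded quantity differ. The purpose is the amount leaked over three coughs; the record is one spot. A woman whose three coughs land in one place has her whole wetted area described. A woman whose coughs land in different places has only part of hers described. Which of these happens plausibly depends on how the towel is held, which has little to do with bladder health. The recorded value can therefore rank two women in the wrong order.

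The loss arises when the data are collected. The extra areas are outlined and then left unmeasured, the number of spots is not recorded, and the towel itself is not said to be kept. The bladder scan and uroflow printouts, by contrast, are taped to forms and filed. No later analysis plan can restore what was not written down.

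A second, smaller matter is the wording. The instruction most naturally means the single largest area, but it could be followed by taking the longest length from one spot and the widest width from another. That pair would describe no spot on the towel.

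**Working it through.** The protocol gives no figure on this point, so there is none to reproduce. The check asks how far the recorded value can depart from the total, and how much that could matter.

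**1. Share recorded.** Treat each spot as an ellipse with area = (π/4) × length × width (an assumption; the protocol gives no area formula). With k equal spots, recorded/total = 1/k:
- two spots: 1/2 = 50%
- three spots: 1/3 = 33%

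**2. Rank reversal is possible.** The spot sizes here are illustrative.
- Woman A, two spots of 30 × 20 mm: each (π/4) × 30 × 20 = 471 mm². Total 942 mm², recorded 471 mm².
- Woman B, one spot of 35 × 25 mm: (π/4) × 35 × 25 = 687 mm², recorded 687 mm².
- A has the larger wetted area but is recorded below B.

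**3. The wording.** Take two spots of 40 × 10 mm and 15 × 30 mm.
- Areas: (π/4) × 40 × 10 = 314 mm² and (π/4) × 15 × 30 = 353 mm². Total 668 mm².
- Largest-spot reading: 353 mm², an under-count.
- Mixed reading (length 40, width 30): (π/4) × 40 × 30 = 942 mm², an over-count.

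**4. Can anything else recover the total?** The overflow tick covers any outlined area but marks only run-off at the towel edge. There is no field for the number of spots or for further dimensions. So it cannot be recovered.

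**5. Likely size across women.** The protocol says only that several spots occur sometimes, and it gives no expected share of women who leak. The following are therefore assumptions:
- lognormal total area with log-SD 0.5 or 1.0
- 10%, 30% or 50% of leaking women with two or three spots
- area divided among spots by a Dirichlet(2) distribution
- recorded value = largest spot; 200,000 simulated women

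On average, women with several spots have about 61% of their area recorded. Spearman correlation of recorded with total area, *leaking women only*:

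| Share with several spots | Spearman | Discordant pairs |
|---|---|---|
| 10% | 0.95–0.985 | 3–5% |
| 30% | 0.88–0.96 | 7–12% |
| 50% | 0.84–0.95 | 9–16% |

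The test is given across the whole clinical sample. This includes a target of 94 women reporting no bladder problems (section IV.C.1.a, Table 1) and women recruited for frequency, pain, flow or infection. Dry towels are recorded correctly. With non-leakers entered at zero, over the same range of several-spot shares:

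| Share leaking (assumed) | Spearman |
|---|---|
| 20% | 0.997–0.9998 |
| 40% | 0.987–0.999 |
| 60% | 0.963–0.997 |

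Pearson correlations are somewhat lower, about 0.94 to 0.99.

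**6. Effect on a BHI correlation.** With a simulated BHI score related to leakage, the rank correlation using the recorded instead of the total area changes as follows:
- 20% leaking, 50% with several spots: 0.248 to 0.247
- 40% leaking, 30% with several spots: 0.291 to 0.287
- 60% leaking, 50% with several spots: 0.319 to 0.310

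The largest fall is 0.319 − 0.310 = 0.009, against a threshold of 0.20.

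**The case against.** A reader might infer that the rule materially weakens the validity evidence. The documents do not support that. No frequency of several spots is given, dry towels are unaffected, and under generous assumptions the correlation with the BHI falls by about 0.01 at most. If spot position is unrelated to bladder health, the error is noise: it pulls correlations down and cannot create false support. The PTT is also only one of several hard measures, alongside post-void residual and uroflow. All of this stands, and it limits the point to a cheap improvement in data collection.

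A reader might also infer that the rule always under-counts. That holds on the plain, largest-spot reading, which the singular wording favours. It need not hold if someone mixes dimensions from two spots. The mixed reading is strained, so it is a reason to tidy the sentence and not a defect in its own right.

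A third tempting step is to treat wetted area as volume leaked. The protocol gives no calibration between the two, and spots from earlier coughs have longer to spread before they are outlined. The percentages above concern area only.

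Finally, the test follows a cited published method. If that method uses a largest-spot rule, keeping it would be a choice for comparability. This cannot be checked from the protocol, which does not itself say that the largest spot is the intended measure. What the objection leaves untouched is the mismatch between purpose and record, and the fact that it cannot be repaired after collection.

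**Conclusion.** The point holds as a mismatch between what the PTT is said to quantify and what the form captures. For women with several spots the recorded value is the largest single spot: 50% of the wetted area with two equal spots, 33% with three, and about 61% on average under the simulation assumptions. The remainder is lost for good.

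The consequence is modest. Leak versus no leak is unaffected. Rank agreement with total area is about 0.84 to 0.985 among leaking women and about 0.96 to 0.999 with dry towels included, so attenuation of BHI correlations is likely small and in the conservative direction. These ranges rest on assumed shares of women who leak and who have several spots, on the assumed spread and division of areas, on elliptical spots, and on spot position being unrelated to bladder health. Confidence is high that the mismatch exists and low about its exact size.

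**What to change.** In section IV.D.5.A and on the Clinical Test Form:

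1. Record length and width for every outlined area (rows 1 to 3, with the largest flagged), taking both dimensions of a row from the same area.
2. Derive the PTT amount centrally as the sum over areas of (π/4) × length × width. Staff still calculate nothing by hand.
3. Keep the largest-area value as a secondary result, for comparison with single-area PTT data.

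If the sponsor prefers the present rule, the minimum is to state that the measure is the largest single spot and to reword the instruction so that length and width clearly come from that one area.

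The cost is two further pairs of form fields and a one-line change in training. The areas are already outlined, so the extra work is under a minute per affected participant. The downside is a possible mismatch with PTT data collected under a single-area rule, which step 3 covers. How to analyse towels marked as overflow is a separate choice and needs no change here.

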presented with. These items are intended to capture respondent perception of their overall bladder health and impact of their bladder on their life. These “universal” items are answerable for every woman independent of the presence of LUTS. The second set of items are designed to capture information regarding presence of LUTS, including impact on activities and quality of life. Therefore, these symptom specific items are only asked of respondents who indicate experiencing one of the 6 LUTS domains (urinary urgency, frequency, incontinence, voiding dysfunction, urinary pain and urinary tract infections). There is a plethora of validated instruments designed to measure severity of LUTS and impact on quality of life, providing a rich pool of item structures to inform the BHI symptom specific item development. Conversely, there is a dearth of validated instruments that measure the constructs or dimensions of bladder health that the BHI universal items intend to measure. While less is known about how women will interpret or respond to these universal items, through the process of community engagement and review of the SHARE transcripts described above, the VIEW team has worked to assure conceptual and linguistic consistency with BHI items. The greater level of scrutiny via the cognitive evaluation of universal items will also allow confidence that items are capturing what they are intended to capture.

The first cognitive evaluation approach is evaluation of item structure and format as well as item order. The online electronic panel (e-panel) provides access to a large sample of female respondents which is necessary to evaluate distributional differences between both item structure of item versions as well as item order. The Bladder Health e-panel evaluates a wide range of issues associated with candidate items in the BHI, including:

- Response formation (exceptions, recall accuracy and deconstruction)
- Item preference (comparison of words and phrases, e.g., frustration v. bothersomeness)
- Response categories and impact of range of options
- Question order and evaluation of location within the instrument
- Item preference

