Where practically possible, the participant-judge interaction will be scheduled to and actually occur prior to the administration of clinical tests. This is needed to minimize potential for test effects to influence participants interaction with the judge. Further, if the tests are performed before the clinical interview, the results may not be provided to the judge until after they have completed the interview and done the initial 1st and 2nd ratings.

Participants recruited from community or from non LUTS practices who report bothersome symptoms and request evaluation and treatment will be referred for clinical care per the individual PLUS research site's practices. For women recruited from LUTS medical practice/clinic, who were already scheduled for a new patient visit, any additional testing and evaluation beyond the clinical tests outlined above may be performed on the same day as the research appointment and will proceed per the provider's usual clinical practice. Information

gained from routine clinical care may be used in conjunction with clinical data collected for research purposes to inform the expert evaluator's 3rd and 4th rating of bladder health.

IV.E. Analyses

All analyses will be conducted on the general population and the clinical evaluation sample separately, data from the different sources will not be pooled. The final factor structure of the BHI scale will be determined based on the general population data. While the clinical evaluation sample data will not be pooled with the general population data, the clinical evaluation sample data provides a cost-effective means of conducting some external validity tests, i.e., it is not feasible to collect data for frequency/volume diaries or clinical evaluation measures or expert evaluator ratings for the general population sample.

IV.E.1. Distribution evaluation

IV.E.1.a. Ceiling and floor effects

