Items will be evaluated for ceiling and floor effects. It is expected that for asymptomatic women many items will demonstrate a pronounced ceiling effect. Therefore, item response of asymptomatic and symptomatic women will be evaluated separately. Within symptomatic respondents, it is expected that those who report mild LUTS will demonstrate greater ceiling effects than respondents who report severe LUTS. Items that exhibit greater than 85% response in the tail of the distribution within severe LUTS respondents will be removed. Comparison will be both between and within mode and between and within sample frames.

IV.E.1.b. Item missing values

Items with missing values, i.e., no response indicated, will be reviewed. A respondent's failure to provide a response to a question item can pose a threat to the scale or sub-scale (dimension or factor specific item grouping) to construct validity. Generally, statistical methods used to evaluate dimensional validity require that a respondent have complete data on all items included in the evaluation for the respondent's values to be included in the analysis. Therefore, where item nonresponse for specific items is high enough (10% or more) to impact the analysis, the nature of missing data will be evaluated. This evaluation will initially consider item location relative to questionnaire layout and design, branching and item applicability, and item sensitivity level or perceived threat to respondent. Where item nonresponse patterns are not explainable by any of these context based effects, a more formal evaluation of the nature of missingness will be considered prior to determining the scale scoring method.

IV.E.2. Reliability and Validity

IV.E.2.a. Internal Validity

Evaluation of internal validity, often referred to as reliability, will include comparison both between and within mode and between and within sample frames. The analysis for the three distinct phases of internal validity evaluation are described below.

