iii. Internal Dimensional validity: The focus of this analysis is to determine if our prior conceptualization of bladder health and the items developed for measuring bladder health, are supported across the entire pool of items. We will accomplish this identification of dimensions of bladder health, analytically indicated by factors, from our data. Factor analytic methods will be used to identify a factor structure of the BHI. While we may hypothesize what the dimensions of bladder health are, *a priori* this cannot be known. Alpha analysis identifies group of items (potential factors) having 'internal reliability', although it does not identify if the underlying relationship between items intended to measure one dimension are differentiated from items intended to measure other dimensions. Therefore, for the dimensions that meet the Alpha threshold ($\alpha \geq .40$), we will run a confirmatory factor analysis to evaluate the actual factor structures against our hypothesized dimensions. While it would be highly unusual for our theorized model to hold up to an initial unrotated factor model, we believe the work on developing a theoretical model of bladder health warrants a preliminary comparison of the model to the data. For the dimensions or factors that do not meet the minimum Alpha criteria, we will run an exploratory factor analysis to identify any systematic and meaningful relationships between groups of these items, that is, if any meaningful factors emerge. Following this we will pool all items together and conduct an exploratory factor analysis.

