Sample sizes are based on several criteria. The basic rule of thumb for psychometric analysis (primarily correlation analyses) is 10 participants per survey item²⁹ although less conservative estimates of 5-10 participants per item³⁰ have been suggest. The BHI contains 2 general categories of question items: those asked of all respondents (global), and those that respondents will be branched into based on response to earlier screening type questions (LUTS-specific). The minimum number of global items under consideration for inclusion the BHI that a respondents could be asked is 53, with an additional 14 items a respondent could be branched into. Therefore the maximum number of global items that will be evaluated for inclusion in the BHI is 67. The number of global items is expected to be substantially reduced through the cognitive evaluation process. The minimum number of LUTS specific items under consideration for inclusion the BHI that a respondent could be asked is 6 (no experience of any LUTS), with up to an additional 12 items a respondent could be branched into, dependent on the number of LUTS experienced. Note it is unlikely that all of the symptom specific items will be applicable to or answerable by all respondents. Therefore, the maximum number of LUTS specific items that could be evaluated for inclusion in the BHI is 18. With a total maximum of all items included for evaluation for inclusion in the BHI being 85, the proposed sample size in aggregate, of n=1202 is sufficient under the most stringent or conservative criterion. Conducting factor analysis on each of the general population sample (n=694) and the clinical evaluation sample (n=508), still provides over 8 and 6 participants per item evaluated, respectively. This estimate is also conservative in that it assumes respondents will have experienced all 6 LUTS and therefore will be branched into the additional 12 LUTS items.

The sampled number of completes will be as follow:

Sample Completes	PAPI	CASI	Total
General Population	333	361	694
Retest	≥75	≥75	200
Clinical			
General	177	177	354
Post Partum			154
Total			1202

IV.F. Informed Consent

IV.F.1 General Population Surveys and Diaries

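### The pooled factor analysis counts every woman as having data on all 85 items, but 26 are branched, so the stated participants-per-item ratios are not attained and the 10% per-item trigger does not bound the loss

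*Protocol*

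**What the plan says.** - **Complete data (IV.E.1.b).** Methods for dimensional validity generally "require that a respondent have complete data on all items included in the evaluation".
- **Trigger (IV.E.1.b).** Missingness is examined "where item nonresponse for specific items is high enough (10% or more) to impact the analysis". The review covers branching: "This evaluation will initially consider item location relative to questionnaire layout and design, branching and item applicability". A further step is reserved for what remains: "Where item nonresponse patterns are not explainable by any of these context based effects, a more formal evaluation" will be considered.
- **Pooled analysis (IV.E.2.a.iii).** After dimension-level models: "Following this we will pool all items together and conduct an exploratory factor analysis". The analysis is then repeated by LUTS level, including women with no LUTS.
- **Branching (III.B).** "these symptom specific items are only asked of respondents who indicate experiencing one of the 6 LUTS domains".
- **Item counts and ratios (IV.E.3).** Global items: 53 asked of all plus 14 branched. LUTS items: 6 asked of all plus up to 12 branched. The total is 85, and the general population (694) and clinical (508) samples are said to give over 8 and 6 participants per item. The section adds: "This estimate is also conservative in that it assumes respondents will have experienced all 6 LUTS".
- **Deciding sample (opening of IV.E).** "The final factor structure of the BHI scale will be determined based on the general population data".

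**The concern.** These statements do not fit together. If complete data are needed on every pooled item, and some items are put only to women with a given symptom, a woman without that symptom cannot be a complete case. The plan notices branching as a reason for nonresponse but attaches no handling rule to it: missingness that branching explains drops out of the formal evaluation. Meanwhile the sample-size section divides the whole sample by the full item count, as if every woman answered everything.

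At stake is the study's main product. The scale is meant to run from very healthy to very unhealthy. A structure estimated on women with every symptom would rest on a small and unrepresentative group, with much less precision than 694 suggests. Separately, a threshold applied item by item says nothing about how many respondents are incomplete on a long instrument.

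**Working it through.** **1. Reproduce the stated figures (IV.E.3).** Items: 53 + 14 + 6 + 12 = 85. General population: 694/85 = 8.16. Clinical: 508/85 = 5.98, so the clinical ratio is just under 6, not over it. Both divide the full sample by all 85 items.

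**2. Branched and always-asked items.** Branched: 14 + 12 = 26. Always asked: 53 + 6 = 59.

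**3. Usable N for the pooled EFA if not-asked items stay blank.** All 12 LUTS follow-ups are reached only with all six LUTS. If q is the share of women with all six, complete cases are at most 694 × q. They would be fewer if some of these women do not reach the 14 branched global items. The protocol gives no value for q, so these are assumptions:

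| q (assumed) | Complete cases of 694 | Per item (÷ 85) |
|---|---|---|
| 1% | 7 | 0.1 |
| 5% | 35 | 0.4 |
| 10% | 69 | 0.8 |
| 20% | 139 | 1.6 |
| 30% | 208 | 2.4 |

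Five per item, the bottom of the less strict 5-10 range cited in IV.E.3, needs 5 × 85 = 425 women, so q = 425/694 = 61%. In the rerun among women without LUTS, q = 0 and no complete cases exist. The by-mode analyses in IV.E.2.b start from 333 and 361; at q = 10% that leaves about 33 and 36.

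**4. Direction of the all-six assumption.** It maximises the denominator (85 items), which is cautious for the item count. It also credits every woman with an answer to every follow-up, which is the most favourable assumption for the numerator.

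**5. Ordinary skips on the 59 always-asked items.** Let m be the skip rate per item, below the 10% trigger throughout.

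- Independent skips: the complete share is (1 − m)^59.
- Clustered skips: beta-binomial with within-person correlation ρ, a = m(1 − ρ)/ρ and b = (1 − m)(1 − ρ)/ρ. The complete share is Γ(b + 59)Γ(a + b) / [Γ(b)Γ(a + b + 59)].

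| m (assumed) | Independent | ρ = 0.1 | ρ = 0.3 |
|---|---|---|---|
| 1% | 384 (55%) | 576 (83%) | 640 (92%) |
| 2% | 211 (30%) | 477 (69%) | 589 (85%) |
| 5% | 34 (5%) | 270 (39%) | 460 (66%) |

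Entries are complete cases of 694. With independent skips, half the sample is lost at m = 1 − 0.5^(1/59) = 1.2%.

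**6. Ratios on the always-asked items.** 694/59 = 11.8 and 508/59 = 8.6, before any skips.

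**Caveat on inputs.** Section IV.D.1 gives 48 items asked only of women with a specific LUTS, against 12 branched LUTS items in IV.E.3. Adding 48 to 53-67 gives 101-115, not 85. The working uses the IV.E.3 counts, on which the stated ratios rest; the two sections need reconciling.

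**The case against.** A reader might infer that the protocol prescribes listwise deletion and will therefore derive the scale from women with all six LUTS. The text does not go that far. The complete-data sentence opens with the word generally and explains why nonresponse is examined; it names no estimator. Missing values are described as a failure to respond, and the protocol never says whether a follow-up that was not asked counts as missing or as symptom absent. That the no-LUTS rerun is planned at all suggests that its authors did not intend an empty analysis. Branching is named in the review, a heavily branched item would exceed 10% if not-asked counts as nonresponse, and detailed coding rules are often left to a statistical analysis plan, which was not available here. All of this stands. It means that the loss depends on an unstated rule, not that the rule exists.

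Three further points limit the concern. Dimension-level models come before the pooled EFA, and those for sections B to E do not need the LUTS follow-ups. Six of the 18 LUTS items go to everyone. And IV.E.3 expects the cognitive evaluation to reduce the global items substantially.

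A reader might also infer that ordinary skips will remove most of the sample. The documents give neither a skip rate nor its clustering; with moderate clustering at 2%, 69% to 85% of women stay complete. The supportable statement is that the trigger can permit a large loss unnoticed.

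Finally, it would be too strong to call the all-six assumption simply backwards. It is conservative for the item count. What does not stand is using it to support a ratio whose numerator remains the full sample.

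**Conclusion.** The point holds in this form. Under the protocol's own general requirement and item counts, the pooled EFA can use at most the women with all six LUTS unless not-asked items are given values, and it can use none in the no-LUTS subgroup. The stated 8 and 6 participants per item are then not attained for that analysis, and the second is 5.98 even with the full sample. The shortfall depends on an unknown: an assumed 10% with all six LUTS gives 69 women and 0.8 per item; an assumed 30% gives 208 and 2.4.

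The 10% per-item trigger does not control cumulative loss. Its practical effect ranges from modest to severe according to the assumed skip rate and clustering.

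The branching part rests on not-asked items remaining blank and on the IV.E.3 counts. The defect is a stated ratio without support and a missing handling rule, not proof that the analysis will fail.

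**What to change.** 1. **Branched items.** Run the all-respondent EFA on the 59 always-asked items and factor the branched follow-ups separately among the women asked them. Alternatively, code a not-asked item as symptom absent, but only where an item-by-item check shows that category is meaningful. For follow-ups on chronicity or history it may not be, and filling a whole block from one gate question builds in correlation among its items.
2. **True nonresponse.** Use full-information or pairwise estimation, or multiple imputation. A blanket ban on complete cases is unnecessary; they may serve as a sensitivity analysis on the always-asked items.
3. **Trigger.** Keep the 10% per-item review and add one on the share of respondents incomplete on the analysed set.
4. **Section IV.E.3.** Restate participants per item on usable N for each analysis (11.8 and 8.6 on the 59 items before skips), remove the sentence calling the all-six assumption conservative, and reconcile the counts with IV.D.1.

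The cost is protocol wording, a short item-by-item coding check and some added analysis code. No data collection or sample size changes. Separate factoring does give up a direct view of how follow-ups load alongside the universal items.
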